8.3. Variables

8.3.1. Exposure definitions

Exposures

• First exposure to any core agent of interest (DTG vs. RPV, RAL, BIC, EVG/c or DRV(/r/c)), after inclusion in the OPERA database. Prior exposure to other core agents of interest is not allowed after inclusion in the OPERA database.

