8.1. Study Design

Study objectives will be evaluated through an observational analysis of a clinical cohort utilizing prospectively-collected EMR data obtained from the OPERA Observational Database. Study participants will be identified from the most recent database build available.

Period of subject inclusion:

- 01AUG2013 (DTG-approval)
- 31DEC2017

Period of observation:

- 01AUG2013 (DTG-approval)
- 31DEC2018

Population:

- A diagnosis of HIV-1, a positive HIV-1 Western Blot, or a positive HIV-1 enzymelinked immunosorbent assay (ELISA); and a detectable HIV-1 viral load test
- At least 18 years of age at the index date
- Male or female
- Prescribed one of the following core agents as part of a 3-drug regimen for the first time between 01AUG2013 and 31DEC2017:
 - DTG (Tivicay[®], Triumeq[®])
 - RPV (Edurant[®], Complera[®], Odefsey[®])
 - RAL (Isentress[®], Isentress HD[®])
 - EVG/c (Vitekta[®], Stribild[®], Genvoya[®])
 - DRV (/r/c) (Prezista[®], Prezcobix[®], Symtuza[®])
 - BIC (Biktarvy[®])
- Not exposed to >1 core agent of interest concurrently

Index date: The index date for an eligible patient is defined as the first date of the first regimen of interest ever prescribed to a patient after 01AUG2013.

Baseline period: The 12-month baseline period preceding the index date will be used to assess patient demographic and clinical characteristics. Data from the visit closest to the index date will be used for analysis.

Observation period: Patients will be observed from their index date until 6,12, and 24 months post-initiation of the regimen of interest, with the final study end date on 31DEC2018.

Censoring events: (i) End of follow-up (6,12, or 24 months after core agent initiation), (ii) cessation of continuous clinical activity*, (iii) core agent discontinuation, (iv) pregnancy, (v) death, or (vi) study end (31DEC2018).

* Continuous clinical activity is defined as at least one clinic visit within a 12month period. Patients failing to meet the continuous clinical activity requirement will be censored 12 months after their last contact.

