8.2. Study Population and Setting

The analysis population will be identified from the OPERA Observational Database according to the inclusion criteria defined below.

Primary population

1) A diagnosis of HIV-1, a positive HIV-1 Western Blot, or a positive HIV-1specific ELISA; and a detectable HIV-1 viral load test

- 2) At least 18 years of age at the index date
- 3) Male or female patients
- 4) Prescribed DTG, RPV, RAL, BIC, EVG/c and DRV(/r/c) as part of a 3-drug regimen for the first time between 01AUG2013 and 31DEC2017
- 5) Not exposed to >1 core agent of interest concurrently

Subjects with the following criteria will be excluded from the study sample:

- 1) HIV-negative
- A diagnosis of HIV-2, a positive HIV-1/HIV-2 Multispot, a positive HIV-2specific ELISA, a positive HIV-2 Western Blot or a detectable HIV-2 viral load test
- 3) Women who are considered pregnant at the index date
- 4) Transgender patients (potential for weight changes due to hormone use)

Secondary population

The study population for the secondary objectives will be a subset of the primary study population meeting the following additional inclusion criteria:

- Patients switching to DTG, RPV, RAL, BIC, EVG/c or DRV(/r/c) as part of a 3-drug regimen for the first time between 01AUG2013 and 31DEC2017 (excluding ARTnaïve patients)
- Patients with a viral load <200 copies/mL at last viral load test prior to switch to core agent of interest

The descriptive primary objective (1) will be stratified by prior ART exposure (ART-naïve and ART-experienced. The primary objective assessing association between core agent and BMI change (2), and the secondary objective will be restricted to ART-experienced patients. ART-experienced will be defined as history of ART prior to initiation of the core agent of interest, or a baseline viral load of <1000 copies/mL.

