8.3.2. Outcomes of Interest

- 1. BMI/weight:
 - Weight (in kg) will be assessed at baseline, and at 6 months, 12 months, and 24 months after core agent initiation
 - BMI will be assessed at baseline, and at 6 months, 12 months, and 24 months after core agent initiation. BMI will be defined as:
 - $BMI = weight/height^2$
 - Weight measured in kg
 - Height measured in m
 - Baseline BMI identified using weight measured within 3 months prior to or on index date
 - BMI categories will be assessed at baseline, and at 6 months, 12 months, and 24 months after core agent initiation (shown in Table 11)
 - Changes in BMI after 6 months, 12 months, and 24 months on the core agent of interest will be calculated as:
 - $\Delta BMI = BMI_n BMI_0$
 - Where BMI_n is BMI at 6, 12, or 24 months and BMI₀ is BMI at baseline
 - Changes in weight after 6 months, 12 months, and 24 months on the core agent of interest will be calculated as:
 - $\Delta Weight = Weight_n Weight_0$

Where Weight_n is weight at 6, 12, or 24 months and Weight₀ is Weight at baseline

- Time windows for BMI and weight
 - BMI/weight at 6 months: BMI measured the closest to 6 months after core agent initiation, between >3 and ≤9 months
 - BMI/weight at 12 months: BMI measured the closest to 12 months after core agent initiation, between >9 and ≤15 months
 - BMI/weight at 24 months: BMI measured the closest to 24 months after core agent initiation, between >21 and ≤27 months
- 2. Total cholesterol/HDL/LDL/triglycerides:

- Lipids (total cholesterol, HDL, LDL, triglycerides) will be assessed at baseline and at 6 months, 12 months, and 24 months after core agent initiation
- Time windows for lipid panels
 - Lipids at 6 months: lipids measured the closest to 6 months after core agent initiation, between >3 and ≤9 months
 - Lipids at 12 months: lipids measured the closest to 12 months after core agent initiation, between >9 and ≤15 months
 - Lipids at 24 months: lipid measured the closest to 24 months after core agent initiation, between >21 and ≤27 months
- Total cholesterol levels¹
 - Normal: < 5.2 mmol/L or <200 mg/dl

 - Borderline Abnormal: ≥ 5.2 to < 6.2 mmol/L or ≥ 200 to < 240 mg/dl
 - Dyslipidemia: ≥ 6.2 to < 7.2 mmol/L or ≥ 240 to < 280 mg/dl
 - Severe dyslipidemia: ≥ 7.2 mmol/L or ≥ 280 mg/dl
- LDL levels¹
 - Normal: < 2.5 mmol/L or <100 mg/dl

 - Borderline Abnormal: ≥ 2.5 to < 3.3 mmol/L or ≥ 100 to < 130 mg/dl
 - Dyslipidemia: ≥ 3.3 to < 4.1 mmol/L or ≥ 130 to < 160 mg/dl

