8.3.3. Study covariates

The following patient demographic and clinical characteristics will be assessed when first entering the healthcare setting at one of the designated clinics or within the 12-month baseline period preceding the index date. Data from the visit closest to the index date will be used for analysis.

Demographic variables

- Age
 - Continuous (years)
 - Categorical:
 - i. 18-25 years old
 - ii. 26-49 years old
 - iii. 50+ years old
- Gender
- Race/ethnicity (Black non-Hispanic, Black Hispanic, non-Black Hispanic, American Indian, Native Hawaiian, Pacific Islander, Asian, White non-Hispanic)
- History of injection drug use (yes/no)
- Marital status (e.g., single, married/domestic partnership, widowed, divorced/separated, unknown)
- Geographic region (i.e., Northeast, Midwest, South, West)
- Payer type (i.e. Medicaid, Medicare, commercial insurance, AIDS drug assistance programs (ADAP)/Ryan White, cash, no payer information available)

Virologic variables

- HIV viral load at baseline
 - Continuous (copies/mL and log₁₀ copies/mL)
 - Categorical (naïve):
 - Low (<10,000 copies/mL)
 - Moderate (≥10,000 to <100,000 copies/mL)
 - High (≥100,000 copies/mL)
 - Missing
 - Categorical (experienced):
 - Undetectable (<50 copies/mL)
 - Suppressed (≥50 to <200 copies/mL)
 - Viremic (≥200 copies/mL)
 - Missing

Immunologic variables

- CD4 cell count at baseline
 - Continuous (cells/μL)
 - Categorical:
 - High (CD4 > 500 cells/μL)
 - Moderately High (CD4 count >350 to ≤500 cells/µL)
 - Moderate (CD4 count >200 to ≤350 cells/µL)
 - Moderately Low (CD4 count >50 to ≤200 cells/µL)
 - Low (CD4 count ≤50 cells/µL)
 - Missing

Clinical variables

- Year of ART initiation
- Length of previous regimen (ART-experienced patients only)
- Time between index and end of follow-up (months)
- AIDS defining illnesses at baseline
- Mortality Risk (VACS Mortality Index)
- Comorbid conditions occurring on or before the index date (including T2DM and thyroid disease)
- HCV and HBV co-infection
- Blood pressure
- Concomitant medications associated with weight gain [31, 32] (these medications will be characterized and considered for inclusion in the statistical adjustment set)
 - Definite:
 - i. Antipsychotics and mood stabilizers
 - chlorpromazine, clozapine, haloperidol, lithium, olanzapine, valproic acid, risperidone, quetiapine
 - ii. Antidepressants
 - phenelzine, tranylcypromine, citalopram, amitriptyline, nortriptyline, mirtazapine, paroxetine

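### First use is judged only from entry to the database and low viral load alone counts as ART experience, so patients already on an agent can enter as new users with an on-treatment baseline BMI

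*Protocol*

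**What the plan says.** Protocol Section 8.3.1 defines the exposure as "First exposure to any core agent of interest (DTG vs. RPV, RAL, BIC, EVG/c or DRV(/r/c)), after inclusion in the OPERA database". Its next sentence, "Prior exposure to other core agents of interest is not allowed after inclusion in the OPERA database", limits the bar on the other agents to the same period.

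Sections 8.1 and 8.2 word first use differently. Section 8.2 requires the agent "as part of a 3-drug regimen for the first time between 01AUG2013 and 31DEC2017", with no look-back period and no restriction to time after entry. Section 8.1 sets the index date at "the first date of the first regimen of interest ever prescribed to a patient after 01AUG2013".

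Section 8.2 defines ART-experienced as "history of ART prior to initiation of the core agent of interest, or a baseline viral load of <1000 copies/mL". Either limb is enough.

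For baseline, Section 8.3.2 states "Baseline BMI identified using weight measured within 3 months prior to or on index date", so a weight taken on the index date qualifies. Section 8.3.3 says that covariates "will be assessed when first entering the healthcare setting at one of the designated clinics or within the 12-month baseline period", so no minimum time in the database is required.

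**The concern.** The outcome of the second primary objective is change in BMI from baseline, so baseline must precede the effect of the agent. If a patient started the agent elsewhere, some of the gain on that agent is already in the baseline weight, and the measured change belongs to a later part of the trajectory.

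The viral load limb makes this a practical route. It adds only patients with no recorded ART history, because the first limb covers everyone else. For them the plan in effect infers earlier ART that it cannot see, and then takes the first recorded prescription as initiation. Nothing stated prevents the unseen ART from being the index agent. The adjustment variables that might help (length of previous regimen, number of prior classes) are unknown for these same patients.

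Section 6.2 says the analysis is meant to support evaluation of a DTG weight-gain signal. The differences of interest are small, so modest contamination matters.

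**Working it through.** **1. Tracing one patient through the rules.** Take a patient who started an agent elsewhere, transfers to a participating clinic with viral load below 200 copies/mL and no recorded ART, and is weighed and prescribed the same agent at the first visit.

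- Exposure (8.3.1): met, because this is the first exposure after entry.
- First-time prescription (8.1, 8.2): met if the earlier use is unrecorded. If it is recorded but falls before entry, 8.3.1 admits the patient while the plain wording of 8.1 and 8.2 would not.
- HIV criterion (8.1, 8.2): met only if some detectable HIV-1 viral load is on record. Its timing is not stated.
- ART-experienced (8.2): met through viral load below 1000 copies/mL.
- Baseline BMI (8.3.2): the index-date weight, taken on treatment.
- Stable-switch subset (8.2, 8.5.2): the viral load condition is met. The text speaks of switching but does not require a documented previous regimen.

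**2. Inputs for size.** The plan gives no figure for contamination, so there is none to reproduce. Section 6.1 gives mean BMI gains at 6 and 12 months in a cited cohort of ART-experienced patients starting a new core agent (kg/m²):

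| Agent | 6 months | 12 months | Months 6-12 (difference) |
|---|---|---|---|
| DTG | 0.18 | 0.30 | 0.12 |
| RAL | 0.17 | 0.24 | 0.07 |
| EVG | 0.21 | 0.23 | 0.02 |
| DRV | 0.32 | 0.41 | 0.09 |
| RPV | 0.06 | 0.06 | 0.00 |

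These means carry ± 0.07 to 0.10, so what follows is illustrative. All contamination shares are assumptions.

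**3. Unequal shares, 12 months.** Assume no such patients in DTG, a share p of 10% to 20% in the comparator, and no further gain in those patients. The comparator mean falls by p × its 12-month gain:

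- RPV: 0.06 × 0.10 = 0.006; × 0.20 = 0.012
- EVG: 0.23 × 0.10 = 0.023; × 0.20 = 0.046
- RAL: 0.24 × 0.10 = 0.024; × 0.20 = 0.048
- DRV: 0.41 × 0.10 = 0.041; × 0.20 = 0.082

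The uncontaminated 12-month DTG-minus-comparator differences are 0.24 (RPV), 0.07 (EVG), 0.06 (RAL) and -0.11 (DRV).

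**4. Equal shares, 6 months.** Let a share p in both groups already be on the agent, and let the gain in months 6-12 stand in for theirs. The observed gain is (1 - p) × (gain 0-6) + p × (gain 6-12). At p = 20%:

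- DTG: 0.8 × 0.18 + 0.2 × 0.12 = 0.168
- DRV: 0.8 × 0.32 + 0.2 × 0.09 = 0.274. DTG - DRV = -0.106, against -0.14 uncontaminated.
- EVG: 0.8 × 0.21 + 0.2 × 0.02 = 0.172. DTG - EVG = -0.004, against -0.03.
- RPV: 0.8 × 0.06 + 0.2 × 0.00 = 0.048. DTG - RPV = 0.120, unchanged.

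At p = 30%, DTG - EVG is 0.162 - 0.153 = +0.009, a change of sign.

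**5. Direction.** For DTG - RPV at 6 months (0.12 uncontaminated), shares of 10% in DTG and 30% in RPV give 0.174 - 0.042 = 0.132. The reverse gives 0.162 - 0.054 = 0.108. The sign of the shift follows the unknown shares.

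**The case against.** The strongest reply is that the protocol already has guards. First-time prescription is an inclusion criterion. The detectable viral load criterion would exclude a patient who transfers in suppressed with no detectable result on record. Section 8.4 describes complete health records, and Section 8.3.3 collects year of ART initiation, length of previous regimen and prior classes, so some history is captured. If an earlier start within the inclusion period is recorded, the index date may fall there. The viral load limb also has a sensible purpose: it keeps probably treated patients out of the ART-naïve stratum. Detailed eligibility rules may sit in analysis specifications that are not shown.

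Much of this stands. A reader might infer that the plan ignores all history before entry, or knowingly admits prevalent users. The text supports neither; it supports only that such patients can enter. But the guards narrow the route without closing it. The first-time wording has no look-back and is limited by 8.3.1. The detectable result has no stated timing, and a low-level result would satisfy it. The conflict lies within the protocol's own eligibility and exposure text, so it is not a detail left for later.

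It is also fair that searching recorded history cannot find unrecorded use. That is why the fix also needs a documented prior regimen or an analysis without the viral-load-only group.

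**Conclusion.** The point holds in limited form. Sections 8.1, 8.2 and 8.3.1 disagree on what first use means. Together with the viral load limb, they let patients already on the agent count as new users with an on-treatment baseline BMI. Those with viral load below 200 copies/mL can also enter the stable-switch subset without a documented switch.

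The number of such patients is unknown. Under the assumptions shown, the 12-month shift is at most about 0.01 (RPV) to 0.08 (DRV) kg/m². At 6 months an equal share of 20% moves DTG-DRV by about 0.03. This is small in absolute terms but not small beside several of the cited between-agent differences.

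Two stronger readings are tempting and not supported:

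- **A loss of up to 0.61 kg/m² per misclassified patient.** This is 0.92 - 0.31, from the cited cohort of patients initiating ART. The comparative objective is restricted to ART-experienced patients, whose whole 12-month gain in the cited cohort is 0.06 to 0.41.
- **A spurious DTG excess, because inclusion opens at DTG approval and older agents have had longer to accumulate users.** Core-agent use recorded after entry is already barred, so time on the market acts only through transfers, and their mix by agent is not given. For BIC, which the protocol calls recently approved, the argument would run the other way.

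**What to change.** 1. Reconcile Sections 8.1, 8.2 and 8.3.1 so that first exposure is judged on all recorded medication history, including history dated before database entry, and the index date follows the same rule.
2. For the comparative primary objective and the stable-switch subset, require a recorded prior regimen that does not contain the index core agent. At minimum, repeat these analyses without patients classed as ART-experienced by viral load alone, and report their number by agent.

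The cost is protocol wording, one eligibility flag and some patients. The number lost cannot be derived from the protocol. The pool in Section 8.5.3 is 17,370 (510 + 6,598 + 6,298 + 3,964), so most strata have room. The underweight stratum does not: it has 510 patients across all agents, and Table 2 asks for 460 at a partial correlation of 0.16. A loss of more than 50 would take it below that row. If that is too costly, the repeated analysis is the better choice for that stratum.

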8.3.2. Outcomes of Interest

- 1. BMI/weight:
 - Weight (in kg) will be assessed at baseline, and at 6 months, 12 months, and 24 months after core agent initiation
 - BMI will be assessed at baseline, and at 6 months, 12 months, and 24 months after core agent initiation. BMI will be defined as:
 - $BMI = weight/height^2$
 - Weight measured in kg
 - Height measured in m
 - Baseline BMI identified using weight measured within 3 months prior to or on index date
 - BMI categories will be assessed at baseline, and at 6 months, 12 months, and 24 months after core agent initiation (shown in Table 11)
 - Changes in BMI after 6 months, 12 months, and 24 months on the core agent of interest will be calculated as:
 - $\Delta BMI = BMI_n BMI_0$
 - Where BMI_n is BMI at 6, 12, or 24 months and BMI₀ is BMI at baseline
 - Changes in weight after 6 months, 12 months, and 24 months on the core agent of interest will be calculated as:
 - $\Delta Weight = Weight_n Weight_0$

Where Weight_n is weight at 6, 12, or 24 months and Weight₀ is Weight at baseline

- Time windows for BMI and weight
 - BMI/weight at 6 months: BMI measured the closest to 6 months after core agent initiation, between >3 and ≤9 months
 - BMI/weight at 12 months: BMI measured the closest to 12 months after core agent initiation, between >9 and ≤15 months
 - BMI/weight at 24 months: BMI measured the closest to 24 months after core agent initiation, between >21 and ≤27 months
- 2. Total cholesterol/HDL/LDL/triglycerides:

- Lipids (total cholesterol, HDL, LDL, triglycerides) will be assessed at baseline and at 6 months, 12 months, and 24 months after core agent initiation
- Time windows for lipid panels
 - Lipids at 6 months: lipids measured the closest to 6 months after core agent initiation, between >3 and ≤9 months
 - Lipids at 12 months: lipids measured the closest to 12 months after core agent initiation, between >9 and ≤15 months
 - Lipids at 24 months: lipid measured the closest to 24 months after core agent initiation, between >21 and ≤27 months
- Total cholesterol levels¹
 - Normal: < 5.2 mmol/L or <200 mg/dl

 - Borderline Abnormal: ≥ 5.2 to < 6.2 mmol/L or ≥ 200 to < 240 mg/dl
 - Dyslipidemia: ≥ 6.2 to < 7.2 mmol/L or ≥ 240 to < 280 mg/dl
 - Severe dyslipidemia: ≥ 7.2 mmol/L or ≥ 280 mg/dl
- LDL levels¹
 - Normal: < 2.5 mmol/L or <100 mg/dl

 - Borderline Abnormal: ≥ 2.5 to < 3.3 mmol/L or ≥ 100 to < 130 mg/dl
 - Dyslipidemia: ≥ 3.3 to < 4.1 mmol/L or ≥ 130 to < 160 mg/dl
 - Severe dyslipidemia: ≥ 4.1 to < 4.9 mmol/L or ≥ 160 to < 190 mg/dl
 - Very severe dyslipidemia: ≥ 4.9 mmol/L or ≥ 190 mg/dl
- HDL levels¹
 - Normal: \geq 1.54 mmol/L or \geq 60 mg/dl
 - Borderline Abnormal: ≥ 1.03 to < 1.54 mmol/L or ≥ 40 to < 60 mg/dl
 - Dyslipidemia: < 1.03 mmol/L or < 40 mg/dl

¹ Cut-offs obtained https://www.nhlbi.nih.gov/files/docs/guidelines/atp3xsum.pdf

- Triglycerides levels¹
 - Normal: < 1.7 mmol/L or <150 mg/dl

 - Borderline Abnormal: \geq 1.7 to < 2.25 mmol/L or \geq 150 to < 200 mg/dl
 - Dyslipidemia: ≥ 2.25 to < 5.64 mmol/L or ≥ 200 to < 500 mg/dl
 - Severe dyslipidemia: ≥ 5.64 mmol/L or ≥ 500 mg/dl
- 3. Lipodystrophy:
 - Existing lipodystrophy: diagnosis of lipodystrophy within 12 months prior to or on index date
 - New lipodystrophy: new diagnosis of lipodystrophy at 6, 12, or 24 months after core agent initiation

A diagnosis of lipodystrophy will be identified in the EMR by searching for diagnosis codes and text consistent with lipodystrophy, lipohypertrophy, lipoaccumulation, hyperadiposity, or lipoatrophy.

Baseline	Follow-up	
Underweight (BMI: <18.5)	Underweight (BMI: <18.5)	
	Normal weight (BMI: 18.5 – 24.9)	
	Overweight (BMI: 25.0 – 29.9)	
	Obese (BMI: ≥30)	
Normal weight (BMI: 18.5 – 24.9)	Underweight (BMI: <18.5)	
	Normal weight (BMI: 18.5 – 24.9)	
	Overweight (BMI: 25.0 – 29.9)	
	Obese (BMI: ≥30)	
Overweight (BMI: 25.0 – 29.9)	Underweight (BMI: <18.5)	
	Normal weight (BMI: 18.5 – 24.9)	
	Overweight (BMI: 25.0 – 29.9)	
	Obese (BMI: ≥30)	
Obese (BMI: ≥30)	Underweight (BMI: <18.5)	
	Normal weight (BMI: 18.5 – 24.9)	
	Overweight (BMI: 25.0 – 29.9)	
	Obese (BMI: ≥30)	

Table 1. Changes in BMI categories

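### The LDL Normal limit is printed as 2.5 mmol/L or 100 mg/dl, which are not the same value, so an LDL of 97–99 mg/dl falls in two categories

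*Protocol*

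**What the plan says.** Section 8.3.2 gives every lipid cut-off twice, in mmol/L and in mg/dl, joined by the word or. It names no governing unit and gives no conversion factor. For LDL the first two categories are "Normal: < 2.5 mmol/L or <100 mg/dl" and "Borderline Abnormal: ≥ 2.5 to < 3.3 mmol/L or ≥ 100 to < 130 mg/dl". The next two are "Dyslipidemia: ≥ 3.3 to < 4.1 mmol/L or ≥ 130 to < 160 mg/dl" and "Severe dyslipidemia: ≥ 4.1 to < 4.9 mmol/L or ≥ 160 to < 190 mg/dl". For total cholesterol the first limit is "Normal: < 5.2 mmol/L or <200 mg/dl".

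The abstract (section 3) lists the lipids among the primary outcomes, both as continuous values and as categories. Section 8.5.1 reports the proportion of tested patients in each lipid category and compares agents pairwise. Section 8.5.2 reports the proportions again for the patients suppressed at switch. Section 8.4 describes the source as health records from US clinics and does not say in which unit lipids are held.

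**The concern.** LDL, HDL and total cholesterol are all concentrations of cholesterol, so one factor should convert all three. The LDL Normal pair implies 100/2.5 = 40.0 mg/dl per mmol/L. The total cholesterol Normal pair implies 200/5.2 = 38.5. If rounding cannot explain the difference, the two halves of the LDL rule draw two different lines, and a patient between them meets two categories that should exclude each other.

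What is at stake is the reported proportion of patients in the lowest LDL categories, for each agent at baseline and at 6, 12 and 24 months. Two programmers who each follow section 8.3.2 to the letter could produce different tables.

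**Working it through.** **Step 1. Test within the protocol.** The only assumption is that all cholesterol fractions share one factor. A printed mmol/L value m with rounding half-width h (0.05 at one decimal, 0.005 at two), paired with g mg/dl, allows factors from g/(m + h) to g/(m − h).

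| Pair (mmol/L, mg/dl) | Factors allowed |
|---|---|
| LDL 2.5, 100 | 100/2.55 to 100/2.45 = 39.22 to 40.82 |
| LDL 3.3, 130 | 130/3.35 to 130/3.25 = 38.81 to 40.00 |
| LDL 4.1, 160 | 160/4.15 to 160/4.05 = 38.55 to 39.51 |
| LDL 4.9, 190 | 190/4.95 to 190/4.85 = 38.38 to 39.18 |
| Total cholesterol 5.2, 200 | 200/5.25 to 200/5.15 = 38.10 to 38.83 |
| Total cholesterol 6.2, 240 | 240/6.25 to 240/6.15 = 38.40 to 39.02 |
| Total cholesterol 7.2, 280 | 280/7.25 to 280/7.15 = 38.62 to 39.16 |
| HDL 1.03, 40 | 40/1.035 to 40/1.025 = 38.65 to 39.02 |
| HDL 1.54, 60 | 60/1.545 to 60/1.535 = 38.83 to 39.09 |

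The first row has no overlap with six of the other eight: all three total cholesterol pairs, both HDL pairs and LDL 4.9/190. A factor of about 38.82 fits every LDL and total cholesterol pair except 2.5/100. The protocol's own figures therefore single out one failing pair.

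**Step 2. Conversion at 38.67 mg/dl per mmol/L.** This factor is a physical constant brought in from outside the protocol.

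| Pair | mmol/L limit in mg/dl | Gap to printed mg/dl | mg/dl limit in mmol/L | Rounds to print? |
|---|---|---|---|---|
| LDL 2.5, 100 | 96.68 | 3.32 | 2.586 | no (2.6) |
| LDL 3.3, 130 | 127.61 | 2.39 | 3.362 | no (3.4) |
| LDL 4.1, 160 | 158.55 | 1.45 | 4.138 | yes |
| LDL 4.9, 190 | 189.48 | 0.52 | 4.913 | yes |
| Total cholesterol 5.2, 200 | 201.08 | −1.08 | 5.172 | yes |
| Total cholesterol 6.2, 240 | 239.75 | 0.25 | 6.206 | yes |
| Total cholesterol 7.2, 280 | 278.42 | 1.58 | 7.241 | yes |
| HDL 1.03, 40 | 39.83 | 0.17 | 1.034 | yes |
| HDL 1.54, 60 | 59.55 | 0.45 | 1.552 | no (1.55) |

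The HDL 1.54 limit misses by one unit in the second decimal, and no whole mg/dl value lies in its gap. At a rounded factor of 39, LDL 3.3/130 fits (130/39 = 3.33) but LDL 2.5/100 still does not (100/39 = 2.56).

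**Step 3. Values classified twice.** 97/38.67 = 2.508 and 99/38.67 = 2.560. Both are at or above 2.5 mmol/L and below 100 mg/dl, so 97–99 mg/dl meets both Normal and Borderline Abnormal. Likewise 128/38.67 = 3.310 and 129/38.67 = 3.336, so 128–129 mg/dl straddles the next line.

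**Step 4. Size if the mmol/L limits were applied.** The protocol gives no LDL distribution, so a normal one is assumed. Share moved at the Normal line = Φ((100 − mean)/SD) − Φ((96.68 − mean)/SD).

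- Mean 105, SD 30: Φ(−0.167) − Φ(−0.277) = 4.3 points.
- Mean 100, SD 25: 5.3 points, the largest over means 90–130 and SDs 25–40.
- Mean 130, SD 25: 2.4 points, the smallest over that range.

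At a factor of 39 the range is 1.8–4.0 points. At the second LDL line, at 38.67, the same grid gives 1.1–3.8 points. If every value is classified in mg/dl, the shift is zero.

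**The case against.** The strongest reply is that mg/dl is plainly the intended unit. Every mg/dl limit is a round number, several mmol/L limits are not, and the data come from US clinics. If values are held and classified in mg/dl, no patient is affected. The choice of unit can also be left to the analysis specifications that section 8.6 mentions. Much of this stands: it makes the practical effect small and possibly nil. It does not make the printed equivalence correct, because the protocol states neither the storage unit nor the governing one.

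A reader might infer more than the documents support.

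- **That the total cholesterol and HDL limits are wrong in the same way.** They are not. The total cholesterol gaps are at most 1.6 mg/dl and every pair rounds to its printed value. The HDL gaps are under 0.5 mg/dl. Rounding still leaves a few whole values with two labels at 38.67 (LDL 159; total cholesterol 200, 201 and 279), which naming one unit would also settle.
- **That spurious lipid category changes would be reported.** Sections 8.5.1 and 8.5.2 plan category-change proportions for BMI only.
- **That the shift can be judged against a standard error from the 17,370 patients in section 8.5.3.** That count is of patients with a baseline BMI, not of those with an LDL result. A difference in definition is also not sampling error.

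**Conclusion.** Wrong as written, and minor. The LDL pair 2.5 mmol/L and 100 mg/dl contradicts the protocol's other cholesterol pairs under any single factor, and rounding does not rescue it. The weaker mismatch at 3.3 and 130 depends on the outside factor of 38.67. It disappears at 38.82 or 39, so it should be described as slightly off rather than as proven from the protocol.

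The effect of 2.4–5.3% of patients at the Normal line is conditional. It rests on an assumed normal LDL distribution and arises only if the mmol/L limits are applied; mixing units would move some part of that share. It should not be read as a number of patients who will in fact be misclassified. With one unit used throughout, the shift largely cancels in comparisons between agents, although the reported proportions still depend on which unit is chosen. The adjusted BMI-change model, the weight outcomes and the continuous lipid results do not use these limits.

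**What to change.** In section 8.3.2, state that mg/dl governs lipid classification and that any record in mmol/L is converted to mg/dl, at a stated factor, before it is categorised. Then delete the LDL mmol/L limits, or correct 2.5 to 2.59 and 3.3 to 3.36 (100/38.67 = 2.586; 130/38.67 = 3.362).

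Deletion is cleaner. Against a limit of 2.59, an unrounded 100 mg/dl (2.586 mmol/L) would still fall on the other side of the line, so corrected limits work only if mg/dl is also named as governing.

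The cost is one sentence, two numbers and at most one conversion line in the program. No data are needed and there is no statistical downside.
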